- 3. Do the improvements in functional mobility, quality of life, pain management, and inflammatory biomarkers in knee OA patients differ between those enrolled in the GLA:D[™] and the JointEffort education and exercise programs?
- 4. How does the cost of the programs compare to health outcomes and how much are participants willing to pay to participate in the GLA:D and JointEffort programs?

OBJECTIVES: The objectives of the proposed study are to 1) assess the association between participation in the GLA: D^{TM} standardized program and functional mobility, quality of life, pain management, and inflammatory biomarkers in knee OA patients, 2) assess the association between participation in the JointEffort individualized program and functional mobility, quality of life, pain management, and inflammatory biomarkers in knee OA patients 3) assess if there are any differences in outcomes between the standardized (GLA: D^{TM}) and individualized (JointEffort) exercise programs, and 4) Assess how the cost of the programs compare to health outcomes and how much patients are willing to pay to participate in the GLA:D and JointEffort programs.

METHODOLOGY:

Study Participants: A convenience sample of 100 participants \geq 50 years of age with a primary care physician or orthopedic surgeon knee OA diagnosis will be included in the study. Specifically, 50 individuals will participate in 1) the GLA:DTM program and 50 sex- and age-matched individuals will participate in 2) the JointEffort program. 100 participants is a conservative estimate based on the ability to detect a moderate effect between study groups (1- β =0.8, α =0.05).

Exercise Programs: The GLA:DTM program consists of 1) pre and post program outcome measurement (self-reported and functional outcomes); 2) 2 1-1.5 hour education sessions including information on OA disease characteristics, treatments and self-help strategies; and 3) a neuromuscular exercise (warm-up,

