circuit training, and cool down) training program administered in 1 hour, small (up to 10 persons) groupbased, supervised sessions twice weekly for 6 weeks. The goal of the exercises is to restore neutral, functional alignment of the legs by building compensatory functional stability and improving sensorimotor control. The JointEffort program consists of: 1) one appointment aimed at individualized program design; 2) a nutritional seminar taught by a registered dietician explaining dietary recommendations for OA patients and inflammatory conditions, including weight loss and/or management; and 3) an individualized exercise (strength and neuromuscular training, balance training, and range of motion exercises) training program administered in 1 hour, small (up to 10 persons) group-based, supervised sessions twice weekly for 6 weeks.

Study Outcomes:

1) Participant Characteristics, Adherence, and Medication Use: Demographic (age, sex, height, weight, and body mass index), comorbidity, attendance, exercise log, and medication use details will be recorded at each visit. Adherence will be measured by exercise program attendance (number of sessions).

2) Self-Reported of Symptoms, Function, Quality of Life, and Cost Questionnaire: The following self-report questionnaires will be completed at baseline, 2, and 12 months: the Knee Injury and Osteoarthritis Outcome Score (KOOS) [8], the Intermittent and Constant Osteoarthritis Pain (ICOAP) Score [9], and the EuroQOL-5 Dimensions (EQ-5D-5L) Score [10]. A cost questionnaire will be used to capture information about your employment status, gross income, insurance coverage, willingness to pay, and health care visit.

3) Disease Knowledge and Arthritis-Related Self-Efficacy: The patient knowledge questionnaire on OA (PKQ-OA) [11] and the arthritis self-efficacy questionnaire [12] will be completed at baseline, 2, and 12 months.

4) Physical Function: All participants will complete the 40m Face-Paced Walk Test and the 30s Chair Stand Test [13] at baseline, 2, and 12 months.

5) Biomarker Analysis: A blood serum sample, collected at baseline, 2, and 12 months will be analyzed to assess for inflammatory biomarkers using a Discovery Assay (42 Custom-Plex human assay) with Luminex[®]xMAP technology (Eve Technologies).

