STATISTICAL ANALYSIS: Descriptive statistics (mean (95% CI), proportion (95% CI) or median (range) will be used report the baseline, 2, and 12 month change in self-report, functional and biomarker outcomes, as appropriate. To account for the matched design, mean within-pair difference (95% CI) will be used to compare treatment groups across outcomes. Finally, conditional logistic regression will be used to assess the relationship between attendance (number of sessions) and 12 month change in each outcome.

SIGNIFICANCE: This project will contribute to the understanding of exercise programming prescription for knee OA patients. If GLA:DTM and/or JointEffort support improvements in functional mobility, quality of life, pain management, and inflammatory biomarkers, it could play a role in the implementation strategy for OA patients within the province. Exercise programming has the potential to be implemented in several sites across Alberta, and thus potentially modifying disease progression and possibly delaying total joint replacement.

PROJECT FLOWCHART:

Baseline Appointment Weeks 1-7 Exercise Program (GLA:D™ Canada or JointEffort)		2 Months Assessment & Questionnaires
TIME POINT	GLA:D™ Canada Group	JointEffort Group
	(Standardized Exercise Program)	(Individualized Exercise Program)
Baseline	 The GLA:D[™] Canada program will be 	1) The JointEffort program will be
Appointment	explained.	explained.
	2) Participants will be asked to complete	2) Participants will be asked to complete
	the questionnaires (KOOS, EQ-5D-5L,	the questionnaires (KOOS, EQ-5D-5L,
	ICOAP, PKQ-OA, the arthritis self-efficacy	ICOAP, PKQ-OA, the arthritis self-efficacy
	questionnaire and the Arthritis Cost	questionnaire and the Arthritis Cost
	Questionnaire Baseline).	Questionnaire Baseline).
	3) Demographics, symptoms,	3) Demographics, symptoms, comorbidities,
	comorbidities, and medication use will be	and medication use will be recorded.
	recorded. 4) Blood draw for biomarker analysis.	4) Blood draw for biomarker analysis.5) Participants will be asked to complete
	5) Participants will be asked to complete	physical function tests (40m Face-Paced
	physical function tests (40m Face-Paced	Walk Test and the 30s Chair Stand Test).
	Walk Test and the 30s Chair Stand Test).	6) Individualized program design.
Weeks 1-7	1) Two education sessions about OA (1-	1) One nutritional seminar taught by a
	1.5 hours each), including the	registered dietician explaining dietary

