
RELEVANCE AND POTENTIAL BENEFIT OF YOUR PROJECT TO BONE AND JOINT HEALTH:

Our long-term objective is to optimize non-operative management and improve the quality of life of individuals with knee OA. The majority of patients with knee OA that are referred to orthopedic surgeons (up to 50-75% from Alberta orthopedic surgeons), do not require total joint arthroplasty at that time or are not appropriate surgical candidates due to the degree of OA seen on plain films (i.e. mild-moderate instead of severe), level of severity of functional disability or dysfunction, or co-morbidities, that prevent suitability or readiness for total joint arthroplasty. Therefore, we need to identify those individuals and optimize their non-operative management, with an emphasis on exercise programming to mediate their OA symptoms. Further, we believe that through neuromuscular exercise programming (in both a group or individualized setting), we can prolong the development of OA symptoms and therefore possibly delay and/or prevent the need for total joint arthroplasty surgery. However, current exercise programming will differ based on their income level, out-of-pocket cost and expected benefit. Collecting information on these factors will help decision-makers choose whether a public, partial subsidy or private funding model will best help patients manage their osteoarthritis.

We propose to do this by evaluating the effectiveness of the GLA:DTM Canada standardized exercise program in Alberta and evaluating the currently implemented JointEffort individualized exercise program. Further to this, we will assess differences between functional mobility, quality of life, pain management, and inflammatory biomarkers for knee OA. The main differences between the programs include the following: 1) the mode of delivery (standardized vs. individualized program), 2) the two education sessions about OA (GLA:DTM), and 3) the nutritional seminar taught by a registered dietician explaining dietary recommendations for OA patients and inflammatory conditions (JointEffort). Evaluating these key components will enable us to determine appropriate exercise prescription management strategies for

individuals with knee OA. If GLA:D[™] and/or JointEffort support improvements in functional mobility, quality of life, and pain management, it could play a role in the implementation strategy for OA patients within the province.

REFERENCES

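### The program comparison for question 3 is unadjusted in a convenience sample matched on sex and age, so systematic differences in other measured baseline factors can bias it

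*Combined protocol and SAP*

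**What the plan says.** METHODOLOGY, Study Participants, describes "A convenience sample of 100 participants": 50 people in GLA:D, and "50 sex- and age-matched individuals will participate in 2) the JointEffort program". It mentions no random allocation and gives no rule for who enters which program.

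OBJECTIVES, item 3, is to "assess if there are any differences in outcomes between the standardized" and individualized programs. Objectives 1 and 2 are worded as associations.

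STATISTICAL ANALYSIS gives one between-program analysis: "To account for the matched design, mean within-pair difference (95% CI) will be used to compare treatment groups across outcomes". It names no covariates and does not state the scale of the difference. The sentence before it says that descriptive statistics "will be used report the baseline, 2, and 12 month change in self-report, functional and biomarker outcomes", and question 3 is about improvements, so change from baseline is the likely reading. The only regression in the section has attendance as its exposure, so it does not adjust the program comparison.

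Study Outcomes, item 1, states: "Demographic (age, sex, height, weight, and body mass index), comorbidity, attendance, exercise log, and medication use details will be recorded at each visit". Item 2 has a cost questionnaire covering "employment status, gross income, insurance coverage, willingness to pay, and health care visit". The PROJECT FLOWCHART places demographics, comorbidities, medication use and the baseline cost questionnaire at the baseline appointment.

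**The concern.** Matching on sex and age controls sex and age. Without random allocation, nothing in the design balances the two groups on BMI, comorbidity, medication use, income or starting severity, beyond what those factors share with sex and age.

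On the change-score reading, the baseline value of the outcome enters by subtraction. That removes a stable difference in level. It does not remove regression to the mean when one group starts systematically worse and both drift towards a common mean. The other factors do not enter at all.

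The comparison is meant to be used: RELEVANCE AND POTENTIAL BENEFIT says the evaluation will inform exercise prescription strategies. As planned, no analysis would show whether an estimated program difference changes once measured baseline differences are taken into account. An adjustment chosen after the data are seen, across several scores and a 42-analyte panel, would be open to selective choice.

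**Working it through.** The documents give no baseline data by program. Only the 50 pairs and the form of the analysis come from the plan; every shift and correlation below is an assumption.

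**1. The plan's own figure.** The total of 100 rests on a moderate effect with power 0.8 and α 0.05. Effect size and sidedness are not given. With 0.5 SD assumed and unpaired groups, n per group = 2(z_α + z_β)²/d²:
- two-sided: 2(1.960 + 0.842)²/0.25 = 63 per group, 126 in total
- one-sided: 2(1.645 + 0.842)²/0.25 = 50 per group, 100 in total

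A two-sided paired calculation with within-pair correlation 0.2 needs 51 pairs. So 100 can be reproduced under some readings only. For scale, 50 per group with a two-sided t test and 80% power detects 0.57 SD. Sample size does not remove confounding, so the rest does not depend on this figure.

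**2. Set-up.** Outcome SD 1, baseline to follow-up correlation ρ, no within-pair correlation, no true program effect. The variance of change is 2(1 − ρ), so the within-pair difference in change has SE = √(4(1 − ρ)/50). At ρ = 0.5 the change SD is 1 and the SE is √(2/50) = 0.20. The chance that the 95% CI excludes zero comes from the noncentral t with 49 df. With no systematic shift it is 5%: chance imbalance is already covered by the planned interval.

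**3. Another baseline factor** (for example BMI or income), shifted by g SD and correlated r with change. Bias = r × g, ρ = 0.5.

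| r | g | bias (SD) | CI excludes zero |
|---|---|---|---|
| 0.2 | 0.2 | 0.04 | 5.4% |
| 0.2 | 0.5 | 0.10 | 7.8% |
| 0.3 | 0.2 | 0.06 | 6.0% |
| 0.3 | 0.5 | 0.15 | 11.4% |

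In simulation, adjusting for the factor brought the bias to 0.00 and the exclusion rate to about 5% in all four cases.

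**4. The baseline outcome, shifted by D, both groups regressing to a common mean.** The unadjusted difference in change is biased by (1 − ρ)D in size.

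| ρ | SE | D = 0.2 | D = 0.5 |
|---|---|---|---|
| 0.3 | 0.237 | 0.14 SD, 8.9% | 0.35 SD, 30.5% |
| 0.5 | 0.200 | 0.10 SD, 7.8% | 0.25 SD, 23.2% |
| 0.7 | 0.155 | 0.06 SD, 6.7% | 0.15 SD, 15.8% |

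Here adjustment for the baseline value removes the bias.

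**5. The same shift, but group means stably different.** Change is equal in both groups, so the planned change score has no bias. Regressing change on baseline, with slope −(1 − ρ), moves the estimate by (1 − ρ)D. At ρ = 0.5 that is 0.10 to 0.25 SD, and the adjusted CI excludes zero 9 to 24% of the time. Steps 4 and 5 mirror each other, and the documents cannot say which applies.

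**6. Precision of an adjusted pair-level regression** with k covariates and n pairs. SE ≈ √[(v/n)(1 + k/(n − k − 2))], where v is the residual variance of the within-pair difference, ρ = 0.5.
- Planned analysis, n = 50: 2.01 × 0.200 = 0.40 SD half-width.
- Four covariates without the baseline outcome, none predicting change (v = 2): 2.01 × 0.209 = 0.42. This is the cautious case; covariates that predict change narrow it.
- Baseline outcome added, k = 5, v = 2(1 − 0.5²) = 1.5: 2.02 × 0.183 = 0.37.
- If 15% of participants lack a covariate (assumed) and their pairs are dropped, 50 × 0.85² = 36 pairs remain. The half-widths become 2.04 × 0.251 = 0.51 (four covariates) and 2.04 × 0.221 = 0.45 (five).

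**The case against.** The evidence for selection between these two programs is thin. The closest text, in RELEVANCE AND POTENTIAL BENEFIT, says that "current exercise programming will differ based on their income level, out-of-pocket cost and expected benefit". That concerns exercise programming in general and leads into a discussion of funding models. A reader might take it as the sponsor's admission that GLA:D and JointEffort attract different people, but it does not say so. The BUDGET also carries instructor costs for both programs, in-kind space and parking. Participant fees are not stated, but this weakens out-of-pocket cost as a reason for entering one program rather than the other. That the study is not randomised is itself an inference from a convenience, matched sample with no allocation method described.

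The sizes are assumed and often small. For BMI or income they are at most 0.15 SD here, and the figures of 23 to 31% need a 0.5 SD shift together with regression to a common mean. A reader might also infer that the change score is a mistake and baseline adjustment the right answer. Step 5 shows otherwise: each is biased in one plausible setting, so the choice between them is not an error in the plan.

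Adjustment has hazards of its own. BMI and medication use are recorded at every visit, and JointEffort teaches weight management, so follow-up values could be affected by the program and must not be used. Two estimates also differ by chance: with no shift and no effect, the unadjusted and the five-covariate estimates lie more than 0.10 SD apart in about 37% of runs. A gap between them is therefore no proof of confounding.

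These objections limit the size of the claim and shape the remedy. They do not supply what is missing, namely any analysis of question 3 that uses the baseline factors the study collects.

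**Conclusion.** The point holds as a possibility of bias. The sole question 3 analysis is unadjusted, matching covers sex and age only, and other relevant baseline factors are measured but unused. That rests on the text and is firm, apart from non-randomisation, which is inferred.

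The size is not known. Under the stated assumptions the spurious difference is 0.04 to 0.15 SD from another covariate. From a shifted baseline outcome with regression to a common mean it is 0.06 to 0.35 SD, with the CI excluding zero about 7 to 31% of the time. The plan's detectable difference is about 0.57 SD (two-sided assumed). These figures also rest on the change-score reading and on 50 complete pairs. A reader might conclude that the comparison is biased or invalid; the documents do not support that, because they show no baseline difference between the programs. The change is a cheap improvement.

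**What to change.** In STATISTICAL ANALYSIS:

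- State that the within-pair difference is of change from baseline, and keep it as the named main estimate for question 3.
- Add a table of baseline characteristics by program.
- Prespecify one supporting adjusted comparison per outcome that keeps the matching and uses only values recorded at the baseline appointment: BMI, comorbidity, medication use and income. For continuous scores, regress the within-pair difference in change on the within-pair differences in these covariates; the intercept is the adjusted program difference. Name a suitable paired model for outcomes summarised as proportions or medians, and say how comorbidity and medication use are scored.
- As a sensitivity analysis, report a version that also includes the baseline outcome value, and say that it rests on a different assumption from the change score.
- State how missing covariates are handled so that pairs are not dropped.
- Report every estimate with its 95% CI, without a rule for declaring disagreement, and word the conclusion as an association between program and outcome.

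Cost: no new data or visits; some added text, two scoring rules and one or two extra models per outcome. The models bring their own assumptions. Precision changes little with complete covariates (half-width 0.37 to 0.42 SD against 0.40) but worsens to about 0.45 to 0.51 SD if missing covariates cut the pairs to 36. Selection on unmeasured factors remains.

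### The within-pair comparison loses a measured participant whenever the matched partner misses the 12-month visit, and the plan gives no way to recover that participant

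*Combined protocol and SAP*

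**What the plan says.** Under Study Participants, the plan describes "A convenience sample of 100 participants": 50 people in GLA:D, while "50 sex- and age-matched individuals will participate in 2) the JointEffort program". The only justification of size is that "100 participants is a conservative estimate", tied to the "ability to detect a moderate effect between study groups" with 80% power and alpha 0.05. No dropout allowance is given.

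Under Study Outcomes, questionnaires, physical tests and blood samples are all scheduled at baseline, 2 and 12 months.

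The STATISTICAL ANALYSIS paragraph has three parts: descriptive summaries; then, to reflect the matching, "mean within-pair difference (95% CI) will be used to compare treatment groups across outcomes"; and finally "conditional logistic regression will be used to assess the relationship between attendance (number of sessions) and 12 month change in each outcome". The last part concerns attendance and does not compare the programs. Nothing says what happens to a pair with one member missing.

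**The concern.** Objective 3, the comparison of the two programs, rests entirely on the within-pair difference. That quantity is undefined for a pair with one missing member. Unless something is added to the plan, someone who attends the 12-month visit contributes nothing to the 12-month comparison if the partner did not attend. The 2-month value of the person who left does not enter that comparison either.

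Two things are at stake. The first is precision: in a study of 100 people with no stated dropout margin, data already paid for are set aside. The second is that, if people leave for reasons visible in their baseline or 2-month results and the pattern differs between programs, the 12-month contrast makes no use of information that could correct for it.

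**Working it through.** **The plan's own figure.** The 100 cannot be verified uniquely, because the moderate effect has no number and neither sidedness nor pair correlation (rho) is stated. Assume a standardized difference of 0.5 and use the normal approximation:

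- Unpaired, two-sided: 2 × (1.96 + 0.842)² / 0.5² = 62.8, so 63 per program.
- Unpaired, one-sided: 2 × (1.645 + 0.842)² / 0.5² = 49.5, so 50 per program.
- Paired, two-sided: 62.8 × (1 − rho), so 63, 51 and 32 pairs at rho = 0, 0.2 and 0.5.

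One-sided unpaired gives 100, and paired with rho = 0.2 gives 102. Neither contains an allowance for dropout.

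**Inputs for the check.** From the documents: 50 per program, read as 50 pairs because the analysis uses within-pair differences. Assumed: dropout q per person of 10% to 30%, the same in both programs and independent within pairs; rho from 0 to 0.5; outcome SD of 1. Matching on age and sex alone makes a low rho plausible, but that is judgement.

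**Who is lost.** Measured per program = 50(1 − q). Complete pairs k = 50(1 − q)². Measured people with no measured partner, s per program = 50q(1 − q), or 100q(1 − q) in all. These are expected values.

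**Variance.** Complete pairs only: 2(1 − rho)/k. Likelihood (GLS) estimate using the k pairs and the s unpaired people per program: 2 / [k/(1 − rho) + s]. The ratio is 1 + s(1 − rho)/k = 1 + q(1 − rho)/(1 − q), and its square root is the ratio of interval widths.

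Example, q = 20% and rho = 0.2: k = 32 and s = 8. Pairs only: 1.6/32 = 0.0500. Everyone measured: 2/(40 + 8) = 0.0417. The ratio is 1.20 and the interval is 9.5% wider.

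| Dropout | Measured per program | Complete pairs | Measured but unused | Variance ratio, rho 0 / 0.2 / 0.5 | Interval wider by, rho 0 / 0.2 / 0.5 |
|---|---|---|---|---|---|
| 10% | 45 | 40.5 | 9 | 1.11 / 1.09 / 1.06 | 5.4% / 4.3% / 2.7% |
| 20% | 40 | 32 | 16 | 1.25 / 1.20 / 1.125 | 11.8% / 9.5% / 6.1% |
| 30% | 35 | 24.5 | 21 | 1.43 / 1.34 / 1.21 | 19.5% / 15.9% / 10.2% |

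**Power**, for a difference of 0.5 SD, two-sided 0.05, pairs only against everyone measured. At rho = 0.2: 71.1% v 74.7% (10% dropout), 60.9% v 68.8% (20%), 49.9% v 62.1% (30%). At rho = 0.5 and 20% dropout: 80.7% v 85.1%.

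**Bias**, by simulation with about 21% dropout and no true difference:

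- Dropout tied to a poor 12-month outcome in one program only: complete-pair bias 0.18, 0.14 and 0.09 SD at rho = 0, 0.2 and 0.5. An unpaired comparison of everyone available has bias of about 0.18 SD throughout.
- The same dropout mechanism in both programs: bias about 0 for both estimators.
- Dropout tied to the observed 2-month value in one program only (assumed 2-to-12-month correlation 0.5 to 0.7, rho 0 to 0.2): complete-pair bias of about 0.1 SD; an estimate that uses the 2-month values has bias of about 0.

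**The case against.** The plan never says that incomplete pairs are dropped. It names an estimator and is silent on missing values, and imputation or re-matching would be compatible with a within-pair difference. This is fair: deletion is implied, not stated. But no such method is mentioned, so the estimator as written leaves those people out.

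The loss may also be modest. Dropout and rho are both assumed. At rho = 0.5 the widening is about half that at rho = 0, and power at 20% dropout remains near 81% for a 0.5 SD difference. Most of the loss then comes from dropout itself: variance rises by 56% with pairs only (1/0.64 = 1.56), but still by 39% with everyone kept (1.5625/1.125 = 1.39). This stands, and it limits how much weight the point can carry.

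A reader might infer that the paired analysis is unbiased only if dropout is unrelated to outcome, or that deleting partners creates the bias. The calculations do not support either. The same outcome-related mechanism in both programs gave almost no bias, and with positive rho the complete-pair estimate was less biased than the unpaired available-case one.

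A reader might also infer that the 2-month data of people who leave are wasted altogether. They still enter the 2-month summaries and, if the partner attended, the 2-month paired comparison. They are lost only to the 12-month contrast.

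Finally, one linear model does not suit every outcome: the plan expects proportions and medians as well as means, and includes a 42-analyte panel. The fix allows for this.

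**Conclusion.** The point holds as one of precision and of unused information. The only stated comparison of the programs omits measured participants at 12 months, by an amount that grows with dropout: 9, 16 or 21 people in expectation at 10%, 20% or 30%. The avoidable widening of the interval is about 3–5%, 6–12% and 10–20% respectively, over rho from 0.5 down to 0. These sizes rest on assumed, independent and equal dropout and on an assumed rho.

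Bias is a possibility, not a finding. It needs dropout that is related to outcome and differs between programs. A model using the 2-month values can reduce it when dropout depends on observed results, but not when it depends on unseen 12-month values.

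The documents do not support the stronger conclusion that the comparison is invalid or that the study is necessarily underpowered. This is a worthwhile and inexpensive improvement.

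**What to change.** Amend the STATISTICAL ANALYSIS paragraph before outcomes are examined:

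1. For continuous outcomes (transformed where skewed, as biomarkers may be), make the main program comparison a linear mixed model on the 2- and 12-month values. Include program, visit, program-by-visit and baseline value; the matching factors, a pair random effect, or both; and a participant random effect. Keep everyone with at least one follow-up. Age and sex overlap heavily with the pair effect, so either way of reflecting the matching is acceptable if chosen in advance.
2. For binary outcomes, use an analogous model that keeps all observed participants.
3. Report the complete-pair mean difference with its 95% CI as a supporting analysis, and state the number of complete pairs at each visit.
4. Add a simple sensitivity analysis for dropout that depends on unseen 12-month values, for example by shifting the assumed outcomes of those missing by a range of amounts, separately by program.

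No new data or visits are needed. The cost is SAP wording, somewhat more analysis work, and reliance on the model and on a missing-at-random assumption, which item 4 is there to test.

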2. Program Instructors: GLA:DTM Canada Exercise Program (based on one class for 10 participants): GLA:DTM Canada Certified Instructors (physiotherapists or certified exercise physiologists): 5 x 1 hour baseline appointment @ \$75/hour = \$375.00; 2 x 1.5 hour group osteoarthritis education sessions @ \$75/hour = \$225.00; 12 x 1 hour exercise sessions @ \$75/hour = \$900.00; 2 x 1 hour follow up testing sessions at 2 months @ \$75/hour = \$150.00; 2 x 1 hour follow up testing sessions at 12 months @ \$75/hour = \$150.00. Total to run 1 GLA:DTM Canada class = \$1,800.00 (i.e. \$360.00/person). Run 5 GLA:DTM Canada classes (aim of n=10 participants per class; n=50) = \$9,000.00.

JointEffort Exercise Program (based on one class for 10 participants): JointEffort Instructors (certified exercise physiologists or certified personal trainers): 5×1.5 hour baseline appointment and program design @ \$45/hour = \$337.50; 1×1 hour group nutritional seminar @ \$75/hour = \$75.00; 11×1 hour exercise sessions @ \$45/hour = \$495.00; 2×1 hour follow up testing sessions at 2 months @ \$45/hour = \$90.00; 2×1 hour follow up testing sessions at 12 months @ \$45/hour = \$90.00. Total to run 1 JointEffort class = \$1,087.50 (i.e. \$199.50/person). Run 5 JointEffort classes (aim of n=10 participants per class; n=50) = \$5,437.50.

Program Instructors Total (5 JointEffort and 5 GLA:D[™] classes, n=100): \$14,437.50.

3. Instructor Training: GLA:D[™] Canada Training: 2 instructors x \$450 = **\$900.00**; JointEffort Training: 5 instructors

x 1 hour (testing protocols) @ \$45/hour = \$225.00. Instructor Training Total: \$1,125.00.

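### Conditional logistic regression is named for quantitative 12-month change scores with no binary response defined, so the attendance analysis cannot be fitted as written

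*Combined protocol and SAP*

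**What the plan says.** All references are to the combined protocol and SAP.

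- **Design (Study Participants).** Fifty people take GLA:D, and "50 sex- and age-matched individuals will participate in 2) the JointEffort program".
- **Outcomes (Study Outcomes).** The list covers KOOS, ICOAP, EQ-5D-5L, the knowledge and self-efficacy questionnaires, a 42-plex serum assay and two performance tests: "All participants will complete the 40m Face-Paced Walk Test and the 30s Chair Stand Test". Attendance is defined thus: "Adherence will be measured by exercise program attendance (number of sessions").
- **Description (Statistical Analysis).** The summaries offered are a mean, "proportion (95% CI) or median (range) will be used report the baseline, 2, and 12 month change" in the self-report, functional and biomarker outcomes.
- **Group comparison (same section).** "mean within-pair difference (95% CI) will be used to compare treatment groups across outcomes".
- **Attendance (same section).** "conditional logistic regression will be used to assess the relationship between attendance (number of sessions) and 12 month change in each outcome".
- **Sessions.** Exercise Programs describes GLA:D as "small (up to 10 persons) groupbased, supervised sessions twice weekly for 6 weeks" and gives JointEffort the same frequency and duration; the Project Flowchart repeats this. Budget item 2 prices JointEffort at "11×1 hour exercise sessions" and GLA:D at 12.

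No section gives a cut-point, a minimal important change or a responder rule for any outcome.

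**The concern.** Conditional logistic regression models a yes/no response within matched sets. The response named here is a change in a score, a timed or counted test, or an assay level. Someone following the sentence would have to invent a threshold for every outcome or switch to another model, and the plan limits neither choice. Because the sentence covers every outcome, including a 42-plex panel, there is much room to choose after seeing the data. At stake is the credibility of any reported link between attendance and benefit.

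**Working it through.** **1. The plan's own figure.** There is none to reproduce. The only design figure, 100 participants, refers to a moderate effect between study groups, not to attendance.

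**2. Model against variables.**

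- Response: 12-month change in questionnaire scores, walk test, chair stands and biomarkers. All are quantitative, and the preceding sentence of the plan handles them as means.
- Explanatory variable: a session count. Swapping the two roles therefore does not supply a binary response.
- The variable that is binary within every pair by design is program. Using it as the response would model program membership, not the relation of attendance to change.

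**3. Software check.** On one simulated data set of 50 pairs, a standard conditional logistic routine stopped with an error when given the continuous change score. It ran once the score was dichotomised. With cut-points of 0, 5, 8, 10, 15 and 20 on that data set, the odds ratio per session was 1.19, 1.16, 1.04, 1.06, 1.36 and 1.39, from 25, 29, 29, 25, 20 and 15 discordant pairs. All p-values exceeded 0.10, so part of this spread is sampling noise. It does show that the estimate depends on a cut the plan does not state.

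**4. Information left after dichotomising.** In 1:1 matching only discordant pairs contribute. With 50 complete pairs, responder proportion p and independent responses (assumed), the expected number is 50 × 2p(1 − p):

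- p = 0.5: 50 × 0.50 = 25
- p = 0.3: 50 × 0.42 = 21
- p = 0.2: 50 × 0.32 = 16

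**5. Illustrative power.** Every input is assumed: 50 complete pairs, attendance–change correlation 0.3, baseline unrelated to change, program and baseline in each model, a median split for the logistic model, and within-pair outcome correlation 0 or 0.3. The mixed model also carries age and sex. Ranges span repeat simulations with slightly different settings.

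| Model | Correlation 0 | Correlation 0.3 |
|---|---|---|
| Conditional logistic, median split | 37–42% | 44–48% |
| Linear, within-pair differences | 53–56% | 68–72% |
| Linear, random pair intercept | 85–86% | 87–89% |

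If 20% of people are lost independently (assumed), 50 × 0.8 × 0.8 = 32 complete pairs remain. Within-pair linear power is then 38 / 50%. The mixed model can still use unpaired completers.

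**6. What the mixed model risks.** Suppose attendance has no effect, but an unmeasured factor shared within pairs explains 10 / 20 / 30% of the variance of both attendance and change (assumed). The random-intercept model then rejects falsely in 15 / 46 / 73% of runs, against 6 / 5 / 4% for the within-pair model. With that factor as a covariate, the random-intercept rate returns to 6 / 5 / 5%.

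**7. Session count.** Twice weekly for 6 weeks is 2 × 6 = 12, against 11 in the JointEffort budget. On a raw count, full attendance at 11 sessions equals one absence from 12 (11/12 = 92%).

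**The case against.** The strongest reply is that the sentence is incomplete rather than wrong. The plan allows change to be summarised as a proportion, and together with a logistic model this suggests dichotomised change, so that only the threshold is missing. A responder analysis may indeed have been intended, and the fix allows for it. But the proportion is one of three descriptive options and is tied to no outcome and no cut. Without a threshold the model still cannot be run.

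A second reply is that medication use, also listed under Study Outcomes, could be yes/no. Its scale is not stated, and it is not among the self-report, functional and biomarker changes that the Statistical Analysis section names. It would not rescue an analysis meant for each outcome.

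A third reply is that the power figures prove nothing about the defect. That stands. The plan does not say that it will dichotomise, and it claims no power here. The simulated data have a linear mean, which favours linear models. The comparison is also not quite size-matched: with no attendance effect and a baseline correlation of −0.4, the conditional likelihood-ratio test rejected in 7.1 / 7.6% of runs.

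A reader might also infer that the within-pair regression is the one correct replacement. The documents do not support that. They describe matching on sex and age only, and both can enter a mixed model. The choice trades precision against protection from unmeasured shared factors.

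**Conclusion.** The point holds: the attendance analysis names a binary-response model for quantitative change and defines no binary response, so it cannot be fitted as written. This rests on the text alone and on no assumed number. Severity is minor to moderate.

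A reader might infer that the trial's main comparison is compromised. It is not: attendance appears in none of the four objectives, and the mean within-pair difference between programs does not use this model. Nor do the documents support the claim that the plan loses a stated amount of power. The figures in the working are illustrations on assumed inputs.

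The 11-versus-12 session discrepancy is a separate, smaller matter. It is relevant here only because attendance is a raw count, and the documents do not show which number applies.

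**What to change.** Replace the sentence with one pre-specified linear model for continuous 12-month change that respects the pairing, and report the attendance slope per session with its 95% CI. Two forms are suitable:

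- **(a) Linear mixed model** with a random pair intercept and terms for attendance, program, baseline value, age and sex. It uses incomplete pairs and is clearly more precise, but can be biased by unmeasured factors shared within pairs.
- **(b) Within-pair regression** of the difference in change (GLA:D minus JointEffort) on the differences in attendance and baseline, with the intercept as the program effect. It is robust to shared pair factors, but uses complete pairs only and loses substantial power.

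Name one as the main analysis; the other can be a sensitivity analysis. Both, as set out, assume a common slope in the two programs, which should be stated.

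If a responder analysis is intended, give the threshold for each outcome in advance and state that only discordant pairs contribute.

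Separately, reconcile the JointEffort session number across Exercise Programs, the Project Flowchart and the Budget. If the sessions offered differ by program, analyse attendance as a proportion of sessions offered.

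The cost is a few sentences of SAP wording and no new data. Results become slopes rather than odds ratios.
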